FDA	Food and Drug Administration
GCP	Good Clinical Practice
HIPAA	Health Insurance Portability and Accountability Act of 1996
HRBFA	Human Research Billing Analysis Form
HIT	Heparin-Induced Thrombocytopenia
HUD	Humanitarian Use Device
ICF	Informed Consent Form
ICU	Intensive Care Unit
IDE	Investigational Device Exemption
IND	Investigational New Drug
IRB	Institutional Review Board
ISTH	International Society of Thrombosis and Haemostasis
KDIGO	Kidney Disease Improving Global Outcomes
LDH	Lactate Dehydrogenase
LMWH	Low-Molecular-Weight Heparin
PHI	Protected Health Information
PI	Principal Investigator

PT	Prothrombin Time
REDCap	Research Electronic Data Capture
RNA	Ribonucleic Acid
RT-PCR	Reverse Transcriptase Polymerase Chain Reaction
SAE	Serious Adverse Event
SC	Subcutaneous
SGOT	Serum Glutamic Oxaloacetic Transaminase
SGPT	Serum Glutamic Pyruvic Transaminase
SUSAR	Suspected Unexpected Serious Adverse Reaction
UFH	Unfractionated Heparin
UIRTSO	Unanticipated Problem Involving Risks to Subjects or Others
VTE	Venous Thromboembolism
VWF	Von Willebrand Factor
WCM	Weill Cornell Medicine

1. Protocol Summary

Full Title:	InterMediate ProphylACTic versus Treatment Dose Anticoagulation in Critically Ill Patients with COVID-19: A Prospective Randomized Study (The IMPACT Trial)
Short Title:	The IMPACT Trial
Clinical Phase:	IV
Principal Investigator:	[name]., M.Sc.
Study Description:	
The purpose of this study is to determine if therapeutic dose anticoagulation (experimental group) improves 30-day mortality in participants with COVID-19 compared to those receiving the intermediate dose prophylaxis (control group). Following screening, subjects will be randomized 1:1 to intermediate dose prophylaxis or therapeutic anticoagulation treatment arms. Treatment will continue for 28 days with longer-term follow-up through 6 months.

Sample Size:	N=186; 93 patients per cohort
Enrollment:	The study will enroll 186 subjects and screen up to 300 subjects
Study Population:	Adult patients with documented COVID-19 infection
Enrollment Period:	6 months
Intervention Description:	
Intermediate Dose Prophylaxis
 
• Enoxaparin 0.5 mg/kg subcutaneously every 12 hours if CrCl \geq 30 ml/min• Enoxaparin 0.5 mg/kg subcutaneously every 24 hours if CrCl less than 30 mL/min• If patient develops acute kidney injury (defined by KDIGO guidelines): unfractionated heparin 7,500 units subcutaneously every 8 hours.• Fondaparinux (if history of HIT) 2.5 mg daily subcutaneously 
Therapeutic Anticoagulation
 
• Unfractionated heparin (UFH) to target anti-Xa level 0.3 – 0.7 IU/mL or aPTT (according to institutional protocol).• Enoxaparin 1 mg/kg subcutaneously every 12 hours• Argatroban (if heparin-induced thrombocytopenia [HIT]), dosed according to institutional protocol.• Fondaparinux (if HIT and CrCl \geq 50 ml/min) dosed by weight:
◦ \geq 100 kg: 10 mg daily◦ < 100 kg but \geq 50 kg: 7.5 mg daily◦ < 50 kg: 5 mg daily
Primary Objective:	To determine if therapeutic anticoagulation improves 30-day mortality in COVID-19 positive patients compared to intermediate dose prophylaxis.

Secondary Objectives:

[figure not shown]
1. To assess if therapeutic anticoagulation reduces the length of ICU stay.
2. To determine if therapeutic anticoagulation reduces the number of documented venous thromboembolism (VTE), arterial thrombosis (stroke, myocardial infarction, other) and micro thrombosis.
3. To evaluate if therapeutic anticoagulation leads to increase major and clinically relevant non-major bleeding events as defined by the International Society of Thrombosis and Haemostasis (ISTH) criteria.

Primary Endpoints: Efficacy Outcomes
Death at 30 days

Secondary Endpoints:

- 1- Length of ICU stay
- 2- Objectively documented pulmonary embolism (PE), proximal deep vein thrombosis (DVT) of the upper or lower extremities, thrombosis of the dialysis, continuous renal replacement (CRRT) filters; micro-thrombosis (skin biopsy), arterial thrombosis (stroke, myocardial infarction, limb ischemia)
- 3- Major bleeding, (as per ISTH guidelines), and clinically relevant non-major bleeding events.

1.1 Schema

1.2 Study Objectives and End Points

1.2.1 Primary Objectives

1. To determine if therapeutic anticoagulation improves 30-day mortality in COVID-19 positive patients compared to intermediate dose prophylaxis.

1.2.2 Secondary Objectives

1. To assess if therapeutic anticoagulation reduced the length of ICU stay.
2. To determine if therapeutic anticoagulation reduces the number of documented venous thromboembolism (VTE), arterial thrombosis (stroke, myocardial infarction other) and micro thrombosis.
3. To evaluate if therapeutic anticoagulation leads to increase major and clinically relevant non-major bleeding events as defined by the International Society of Thrombosis and Haemostasis (ISTH) criteria.

1.2.4 Primary Endpoints

Efficacy Outcomes:

1. Death at 30 days

1.2.5 Secondary Endpoints

Safety Outcomes:

1. Length of ICU Stay
2. Objectively documented pulmonary embolism (PE), proximal deep vein thrombosis (DVT) of the upper or lower extremities, thrombosis of the

dialysis, continuous renal replacement (CRRT) filters, micro-thrombosis (skin biopsy), or arterial thrombosis (stroke, myocardial infarction, limb ischemia)

3. Major bleeding, defined (as per ISTH guidelines) as acute clinically overt bleeding associated with one or more of the following:
 - a. A decrease in hemoglobin of 2 g/dL or more;
 - b. A transfusion of 2 or more units of packed red cells;
 - c. Bleeding that occurs in at least one of the following critical sites:
 - i. Intracranial
 - ii. Intra-spinal
 - iii. Intraocular (within the corpus of the eye; thus, a conjunctival bleed is not an intraocular bleed)
 - iv. Pericardial
 - v. Intra-articular
 - vi. Intramuscular with compartment syndrome
 - vii. Retroperitoneal
 - d. Bleeding that is fatal;
 - e. Bleeding that necessitates surgical intervention.

OR Clinically relevant non-major bleeding event, defined as acute clinically overt bleeding that does not meet the criteria for major and consists of;

- f. Any bleeding compromising hemodynamics;
- g. Spontaneous hematoma larger than 25cm², or 100cm² if there was a traumatic cause;
- h. Intramuscular hematoma documented by ultrasonography;
- i. Epistaxis or gingival bleeding requiring tamponade or other medical intervention or bleeding from venipuncture for >5 minutes;
- j. Hematuria that was macroscopic and was spontaneous or lasted for more than 24 hours after invasive procedures;
- k. Hemoptysis, hematemesis, or spontaneous rectal bleeding requiring endoscopy or other medical intervention;
- l. Clinically relevant bleeding defined as the composite of major and clinically relevant non-major bleeding;
- m. Permanent early discontinuation of the anticoagulant due to safety reasons

2. Background

2.1 Disease

The SARS-COV-2 (COVID-19) pandemic has had an unprecedented effect on our healthcare system and led to the death of over 164,939 people worldwide. Within the United States, New York State and specifically New York City has the highest number of COVID-19 infected patients. Why the pandemic carries a relatively high mortality rate across the world remains unclear, but there is growing evidence that COVID-19 triggers a hypercoagulable

state causing mostly microvascular thrombosis. A retrospective study in China showed that critically ill patients with markedly elevated D-Dimers who were on heparin or low-molecular weight heparin (LMWH) prophylactic-dose had lower mortality compared to those who did not receive pharmacologic thromboprophylaxis. At our own institution, pulmonary micro thrombi have been observed on autopsies and numerous skin biopsies of retiform purpura lesions on these patients have revealed thrombotic vasculopathies. In some countries, the dose of heparin or LMWH is being escalated to a therapeutic dose. Whether therapeutic-dose anticoagulation improves outcomes in these critically ill COVID-19 patients has not been studied.

2.2 Investigational Agent

All of the drugs described in this protocol are FDA approved for the intended indications and can be obtained through a prescription.

Enoxaparin (Lovenox®) is an anticoagulant medication approved by the FDA for the prophylaxis and treatment of deep vein thrombosis and pulmonary embolism. Enoxaparin is available as an injectable and is delivered subcutaneously. For this study, subjects randomized to the intermediate dose prophylaxis arm will receive Enoxaparin 0.5 mg/kg subcutaneously every 12 hours if their creatinine clearance is \geq 30 ml/min. Subjects with creatinine clearance of < 30 ml/min will receive Enoxaparin 0.5 mg/kg subcutaneously every 24 hours. Subjects randomized to the therapeutic anticoagulation arm will receive Enoxaparin 1 mg/kg subcutaneously every 12 hours if their creatinine clearance is \geq 30 ml/min and 1 mg/kg subcutaneously every 24 hours if creatinine clearance of < 30 ml/min.

Heparin sodium (unfractionated heparin) is an anticoagulant indicated for the prophylaxis and treatment of venous thromboembolism. For this study, subjects on the intermediate dose prophylaxis arm who develop acute kidney injury, as defined by the KDIGO guidelines, may receive unfractionated heparin 7,500 units subcutaneously every 8 hours. Subjects on the therapeutic anticoagulation arm may receive unfractionated heparin intravenous continuous infusion to target anti-Xa level of 0.3 – 0.7 IU/mL or therapeutic range aPTT, according to institutional guidelines.

Argatroban is a synthetic direct thrombin inhibitor that is approved for the prophylaxis and treatment of thrombosis in adult patients with heparin-induced thrombocytopenia (HIT). Subjects randomized to the therapeutic anticoagulation arm with a history of HIT may receive argatroban dosed according to institutional protocol.

Fondaparinux (Arixtra®) is a synthetic and specific inhibitor of Factor X (Xa) indicated for the prophylaxis and treatment of deep vein thrombosis or acute pulmonary embolism. Subjects randomized to the intermediate dose prophylaxis arm with a history of HIT will receive fondaparinux 2.5 daily subcutaneously. Subjects randomized to the therapeutic anticoagulation arm with a history of HIT and creatinine clearance of \geq 50 ml/min may receive fondaparinux dosed according to weight: if \geq 100 kg, 10 mg daily subcutaneously; if < 100 kg but \geq 50 kg, 7.5 mg daily subcutaneously; if < 50 kg, 5 mg daily subcutaneously.

More information about these agents may be obtained through their package inserts; see Appendix A for further details.

The researchers are requesting an IND exemption for this study as it involves off-label use of FDA-approved medications and will not be applying for a label change.

2.3 Rationale

Venous thromboembolism is a common complication in critically ill patients. Recent publications have demonstrated that the risk of thrombosis (venous, arterial and microthrombosis) in ICU patients with COVID-19 is 31% in a study from Holland despite prophylactic anticoagulation and 25% (venous thrombosis) in a study from China (without prophylactic anticoagulation). In a prospective cohort study from France, there were sixty-four clinically relevant thrombotic complications diagnosed in 150 patients with COVID-19 ARDS during their ICU stay, mainly pulmonary embolisms (25 patients, 16.7%). Based on above published data, we will compare 2 doses of parenteral anticoagulation (intermediate and therapeutic dose) in critically ill patients with COVID-19 infection.

In this study, intermediate dose prophylaxis will be considered the standard of care arm based on experience from the ICU at Weill Cornell Medicine and published data on standard prophylactic dose anticoagulation. The therapeutic anticoagulation arm will be considered experimental.

The D-dimer entry criteria of greater than or equal to 6 times the upper limit or normal was chosen based on published data from Cui et al. D-Dimers are checked on a daily basis as it is being done now in the ICU at WCM.

2.4 Risk/Benefit Assessment

2.4.1 Known Potential Risks

Enoxaparin, heparin, argatroban and fondaparinux are FDA approved parenteral anticoagulants used to prevent and treat VTE. The main side effect of anticoagulation is bleeding, therefore close monitoring of anticoagulation is required.

Further risks and known side effects of the various anticoagulants being used in this protocol may be found in the package inserts, located in Appendix A.

2.4.2 Known Potential Benefits

Critically ill patients with COVID-19 have an increased risk of death, but some studies have shown evidence that this risk has been decreased with the use of parenteral anticoagulation. We believe there will be a lower risk of VTE and other thrombotic events with the use of intermediate dose prophylaxis and therapeutic dose anticoagulation.

2.4.3 Assessment of Potential Risks and Benefits

Hospitalized patients typically receive standard-dose prophylactic anticoagulation to prevent the risk of developing thrombosis throughout their admission. From

April 5, 2020 patients who have required ICU-level care for treatment of COVID-19 in our hospital have been receiving intermediate dose prophylactic anticoagulation due to the observation of higher thrombosis risk noted in critically ill COVID-19 infected patients. Therapeutic dose anticoagulation may be warranted providing that the benefits outweigh the bleeding risk. We hope that this study will provide evidence that higher dose (therapeutic) anticoagulation is more efficacious and as safe as intermediate dose prophylaxis for prevention of thrombosis in critically ill patients with COVID-19 infection.

2.5 Correlative Studies Background

Additional blood will be collected for correlative studies to further assess the pathophysiology of thrombosis in these patients including: thrombin generation assay, plasmin generation, platelet activation assay, clot lysis time, annexin2.

3. Study Design

3.1 Overall Design

Prospective phase IV, open-label randomized control trial comparing two different doses of parenteral anticoagulation (Intermediate vs. therapeutic dose) in critically ill patients with COVID-19 infection. The purpose of the study is to determine if therapeutic dose anticoagulation improves 30-day mortality in COVID-19 positive patients compared to intermediate dose prophylaxis. Patients will be randomized 1:1 to either intermediate dose prophylaxis (standard of care arm) or therapeutic-dose anticoagulation (experimental arm). Each arm will enroll 93 patients, for a total of 186 patients. Treatment on both arms will be for 28 days continuously. Patients will enter the study at the time of hospital admission. Patients will be recruited by their treating physician in the hospital or by the principal investigator.

Intermediate dose prophylaxis:

- If CrCl \geq 30 ml/min, Enoxaparin 0.5 mg/kg SC every 12 hours
- If CrCl less than 30 ml/min, Enoxaparin 0.5 mg/kg SC every 24 hours
- If patient develops acute kidney injury (defined by KDIGO guidelines): unfractionated heparin 7,500 units SC every 8 hours
- If patient has a history of HIT, Fondaparinux 2.5 mg daily subcutaneously

For patients receiving Enoxaparin, adjust dose based on anti-Xa activity 4 hours after 3rd dose; goal of 0.4 – 0.6 IU/mL for intermediate prophylactic dose.

Therapeutic anticoagulation:

Full dose parenteral anticoagulation per institutional protocol:

- Enoxaparin 1 mg/kg SC every 12 hours If CrCl equal or more than 30 mL/min to target peak anti-Xa level 4 hours after the 3rd dose; goal 0.6 - 1.0 IU/mL
- Enoxaparin 1 mg/Kg SC every 24 hours If CrCl less than 30 mL/min to target peak anti-Xa level 4 hours after the 3rd dose; goal 0.6 - 1.0 IU/m
- If patient develops acute kidney injury (defined by KDIGO guidelines): Unfractionated heparin (UFH) to target anti-Xa level 0.3 – 0.7 IU/mL or aPTT (according to institutional protocol)

- If patient has a history of HIT or develops HIT:
 - Fondaparinux (if CrCl \geq 50 ml/min).
 - If patient weight is \geq 100 kg, 10 mg daily
 - If patient weight is $<$ 100kg but \geq 50 kg, 7.5 mg daily
 - If patient weight is $<$ 50 kg, 5 mg daily
 - Or Argatroban if CrCl $<$ 50 ml/min), dosed according to institutional protocol.

Therapeutic dose adjusted per NYP Infonet protocols.

3.2 Scientific Rationale for Study Design

The risk of thrombosis in ICU patients with COVID-19 is 31% in a study from Holland despite prophylactic anticoagulation and 25% in a study from China (without prophylactic anticoagulation) and 43% in a French study despite prophylactic anticoagulation. Therefore we will compare 2 doses of parenteral anticoagulation (intermediate and therapeutic dose) in critically ill patients with COVID-19 infection.

3.3 Justification for Dose

We will compare an intermediate dose (high prophylactic-dose) vs. therapeutic dose anticoagulation in COVID-19 critically ill patients because significant risk of thrombosis was still observed with the standard prophylactic dose of anticoagulation.

3.4 End of Study Definition

A participant is considered to have completed the study if he or she has completed all phases of the study including the last visit or the last scheduled procedure shown in the **Schedule of Assessments (SoA), Section 6.1**. The end of the study is defined as completion of the last visit or procedure shown in the SoA in the trial globally.

4. Subject Selection

4.1 Study Population

Adult subjects with COVID-19 infection will be eligible for this study.

4.2 Inclusion Criteria

1. Age $>$ 18 years old
2. COVID-19 positive on RT-PCR nasopharyngeal swab, or suspected COVID-19 infection with detectable SARS-CoV-2 IgG or IgM.

NOTE: COVID-19 will be defined according to the World Health Organization (WHO) case definition for a “confirmed case”, which is a positive laboratory test for SARS-CoV-2, irrespective of clinical signs and symptoms. WHO reference laboratories currently use reverse transcription polymerase chain reaction (RT-PCR) tests to detect the presence of SARS-CoV-2 viral RNA.

3. ICU patient or non-ICU patient on invasive mechanical ventilation, BiPAP, 100% non-rebreather mask, or high-flow O₂, or supplemental O₂ of at least 4 liters per minute nasal cannula.
4. D dimer \geq 700 ng/mL (3 times the upper limit of normal)

4.3 Exclusion Criteria

1. Objectively documented deep vein thrombosis or pulmonary embolism.
2. Patients in whom there is very high suspicion for pulmonary embolism and are on full-dose anticoagulation as per the treating physician.
3. Platelets <30,000 not due to disseminated intravascular coagulation (DIC), based on ISTH criteria and ASH FAQ (Appendix B).
4. Active bleeding that poses a contraindication to therapeutic anticoagulation in the opinion of the investigator.
5. History of bleeding diathesis (e.g., hemophilia, severe von Willebrand Disease, severe thrombocytopenia)
6. History of intracranial hemorrhage in the last 90 days
7. History of ischemic stroke in the past 2 weeks
8. Major neurosurgical procedure in the past 30 days
9. Cardiothoracic surgery in the past 30 days
10. Intra-abdominal surgery in the past 30 days
11. Intracranial malignancy
12. Patients who require therapeutic anticoagulation for other reasons like atrial fibrillation, deep venous thrombosis, pulmonary embolism, or antiphospholipid syndrome.

4.4 Lifestyle Considerations

Not applicable

4.5 Screen Failures

Screen failures are defined as participants who consent to participate in the clinical trial but are not subsequently randomly assigned to the study intervention or entered in the study. A minimal set of screen failure information is required to ensure transparent reporting of screen failure participants, to meet the Consolidated Standards of Reporting Trials (CONSORT) publishing requirements and to respond to queries from regulatory authorities. Minimal information includes demography, screen failure details, eligibility criteria, and any serious adverse event (SAE).

Individuals who do not meet the criteria for participation in this trial (screen failure) because of a D-dimer level of <1400 ng/mL may be rescreened. Rescreened participants should be assigned the same participant number as for the initial screening.

5. Registration Procedures

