6.1 Schedule of Assessments

See Table 1. Schedule of trial events.

Table 1. Schedule of trial events

	Screening (within 48 hours of treatment initiation)	Randomization	Treatment					30 days post- treatment (+/- 2 days)	60 days post- treatment (+/- 2 days)	Follow-Up
			Day 1	Day 7	Day 14	Day 21	Day 28			
Treatment ⁶			X----->							
Informed Consent	X									
Randomization		X								
Demographics	X									
Medical History ¹	X									
Treatment Initiation			X							
Vital Signs ²	X		X	X	X	X	X	X	X	X
CBC w/ diff, platelets	X		X	X	X	X	X	X	X	X
PT, aPTT	X		X	X	X	X	X	X	X	X
D-Dimer	X		X	X	X	X	X	X	X	X
Fibrinogen	X		X	X	X	X	X	X	X	X
Serum Chemistry ³	X		X	X	X	X	X	X	X	X
FVIII/VWF ⁴		X					X		X	X
Activated Protein C Resistance		X					X		X	X
Lupus Anticoagulant aPTT lupus insensitive		X							X	X
Anticardiolipin		X							X	X
Anti-B2 Glycoprotein-1		X							X	X
Correlative Samples ⁵		X							X	X
Vital Status								X	X	X
Adverse Event Evaluation	X	X	X----->							
Concomitant Medications	X	X	X----->							

1. Including information on symptoms of VTE, site and confirmatory tests, arterial thrombosis or microvascular thrombosis, type of anticoagulant/antiplatelet treatment and other treatment.

2. Body weight, blood pressure, heart rate, O2 saturation, mechanical ventilation, Bi-PAP, high flow O2, 100% non-rebreather mask (as applicable).

3. Albumin, alkaline phosphatase, total bilirubin, bicarbonate, BUN, calcium, chloride, creatinine, glucose, LDH, potassium, total protein, SGOT [AST], SGPT [ALT], sodium

4. VWF (von Willebrand Factor)

5. Two 3mL blue sodium citrate tubes. Randomization sample will be drawn prior to initiation of study treatment.

6. Treatment will be given every day for Day 1-Day 28; see section 7.7 for specific dosing schedules.

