6.1.1 Screening and Randomization

6.1.1.1 Screening (within 48 hours of treatment initiation)

- Informed Consent
- Medical history, including information on symptoms of VTE, site and confirmatory tests, arterial thrombosis or microvascular thrombosis, type of anticoagulant/antiplatelet treatment and other treatment.
- Demographics
- Vital Signs (body weight, blood pressure, heart rate, O₂ saturation, mechanical ventilation, Bi-PAP, high flow O₂, 100% non-rebreather mask [as applicable])
- Labwork (results must be available prior to enrollment and randomization)
 - CBC w/ diff, platelets
 - PT, PTT
 - D-dimer
 - Fibrinogen
 - Serum Chemistry (albumin, alkaline phosphatase, total bilirubin, bicarbonate, BUN, calcium, chloride, creatinine, glucose, LDH, potassium, total protein, SGOT [AST], SGPT [ALT], sodium)
- Adverse Event Evaluation
- Concomitant Medications

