7.7 Dosing and Administration

All subjects will be dosed continuously for 28 days. Specific dosing instructions per drug and per arm are as follows:

Intermediate Dose Prophylaxis arm:

Subjects randomized to the Intermediate Dose Prophylaxis arm will receive one of the following treatments:

- If CrCl \geq 30 ml/min, Enoxaparin 0.5 mg/kg subcutaneously every 12 hours
- If CrCl less than 30 ml/min, Enoxaparin 0.5 mg/kg subcutaneously every 24 hours
- If patient develops acute kidney injury (defined by KDIGO guidelines): unfractionated heparin 7,5000 units subcutaneously every 8 hours.
- If patient has history of HIT, fondaparinux 2.5 mg daily subcutaneously

For subjects receiving Enoxaparin, adjust dose based on anti-Xa activity 4 hours after the 3rd dose; goal of 0.4 – 0.6 IU/mL.

Therapeutic Anticoagulation arm:

Full dose parenteral anticoagulation per institutional protocol:

- Enoxaparin 1 mg/kg subcutaneously every 12 hours if CrCl \geq 30mL/min.
- Enoxaparin 1 mg/kg subcutaneously daily if CrCl <30 mL/min.
- If AKI develops, Unfractionated heparin (UFH) to target anti-Xa level 0.3 – 0.7 IU/mL or aPTT (according to institutional protocol).
- Argatroban (if heparin-induced thrombocytopenia [HIT] and CrCl <50 ml/min), dosed according to institutional protocol.
- Fondaparinux (if HIT and CrCl \geq 50 ml/min), dosed according to patient weight:
 - \geq 100 kg: 10 mg daily
 - <100 kg but \geq 50 kg: 7.5 mg daily
 - <50 kg: 5 mg daily

Therapeutic dose adjusted per NYP Infonet protocols.

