7.11 Measures to Minimize Bias: Randomization

Blocked randomization will be performed in the study. A series of blocks with random block sizes will be generated with a 1:1 allocation ratio to allow for an equal number of

patients in the intermediate dose prophylaxis arm and therapeutic anticoagulation treatment arm. Patients will not be stratified. The block randomization scheme will be provided by a biostatistician not directly involved in the analysis of the study and uploaded to the REDCap randomization module. Randomized assignments will be generated in REDCap after all eligibility criteria have been met. Blinding is not relevant as the study is open-label.

8. Study Intervention Discontinuation and Participant Discontinuation/Withdrawal

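### The protocol gives two incompatible D-dimer entry thresholds (700 and 1400 ng/mL), and the dosing section prints a malformed heparin figure

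*Combined protocol and SAP*

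**What the plan says.** **D-dimer.** Three current sections state or presuppose an entry threshold.

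- Section 4.2, criterion 4, sets the minimum at "700 ng/mL (3 times the upper limit of normal").
- Section 4.5 allows rescreening of people who "do not meet the criteria for participation in this trial (screen failure) because of a D-dimer level of <1400 ng/mL".
- Section 2.3 explains the choice: "The D-dimer entry criteria of greater than or equal to 6 times the upper limit or normal was chosen based on published data".

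Two other sections make the value operative. Screening laboratory work, which includes D-dimer, carries the condition "results must be available prior to enrollment and randomization" (6.1.1.1). Section 7.11 says "Randomized assignments will be generated in REDCap after all eligibility criteria have been met".

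**Heparin, intermediate arm, acute kidney injury.** Section 7.7 prints "unfractionated heparin 7,5000 units subcutaneously every 8 hours". The protocol summary and section 2.2 print "unfractionated heparin 7,500 units subcutaneously every 8 hours", and section 3.1 gives the same 7,500 figure with the route abbreviated. Footnote 6 of the schedule of assessments directs readers to 7.7: "see section 7.7 for specific dosing schedules". Section 7.7.1 also refers back to 7.7 for dose modification.

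**Enoxaparin, therapeutic arm (minor).** Sections 2.2, 3.1 and 7.7 split the schedule at a creatinine clearance of 30 mL/min. The summary lists only the 12-hourly schedule, without the split.

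**The concern.** An eligibility criterion needs one value. As written, a screener working from 4.2 would randomise a patient with a D-dimer of, say, 900 ng/mL. A screener working from 4.5 would log the same patient as a screen failure and might rescreen later. Who is enrolled, and the screen-failure counts that 4.5 requires for CONSORT reporting, then depend on which page was consulted. The stated justification is affected too. The only reason the protocol gives for its D-dimer criterion is the published study cited in 2.3, and that reason is attached to the higher threshold.

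The heparin figure matters because of where it sits. It is not a valid number as printed, and it is in the section to which sites are sent for dosing.

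**Working it through.** **D-dimer: two laboratory scales, or two thresholds?**

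Inputs: 700 ng/mL and 3 × ULN (4.2); 1400 ng/mL (4.5); 6 × ULN (2.3).

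1. ULN implied by 4.2: 700 / 3 = 233.3 ng/mL.
2. The 2.3 criterion on that scale: 6 × 233.3 = 1400 ng/mL. This reproduces the 4.5 figure exactly.
3. ULN implied by pairing 4.5 with 2.3: 1400 / 6 = 233.3 ng/mL, the same as in step 1.
4. Ratio of the thresholds: 1400 / 700 = 2.0.

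The three statements therefore reduce to two thresholds on one scale. A different assay or unit would not give the same ULN from both pairs. Step 3 is an inference, since 4.5 gives no multiple and 2.3 gives no concentration, but the exact agreement makes another explanation unlikely.

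| D-dimer (ng/mL) | By 4.2 | As 2.3 and 4.5 describe it |
|---|---|---|
| below 700 | not eligible | not eligible |
| 700 to 1399 | eligible | not eligible; may be rescreened |
| 1400 or more | eligible | eligible |

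Only the middle row is in dispute. One statement (4.2) supports the lower threshold and two (2.3 and 4.5) the higher.

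**Heparin: comparison of the four statements.**

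| Section | Figure printed (units, every 8 hours) |
|---|---|
| Protocol summary | 7,500 |
| 2.2 | 7,500 |
| 3.1 | 7,500 |
| 7.7 | 7,5000 |

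One of four is malformed, by one extra digit. If the comma were ignored, the digits would read 75,000, and 75,000 / 7,500 = 10 times the figure printed elsewhere.

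**Enoxaparin.** Three of four statements (2.2, 3.1, 7.7) carry the creatinine-clearance split; the summary does not.

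**The case against.** The strongest reply is that the sections do not carry equal weight. Section 4.2 is the inclusion list, and the check before randomisation in 7.11 naturally refers to 4.2 and 4.3. Section 2.3 is background, and the sentence in 4.5 is permissive. Read strictly, it covers only people who have already failed the criteria, so a patient at 900 ng/mL who meets 4.2 never comes under it. That lowers the chance of confusion in practice but does not remove the defect. The 4.5 sentence makes sense only if the cut-off is 1400 ng/mL. If 4.2 governs, 4.5 misdescribes who fails screening and 2.3 justifies a criterion the trial does not use. If the higher figure governs, 4.2 itself is wrong. Text has to change either way.

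It is also fair to say that D-dimer eligibility is settled before randomisation. The ambiguity applies to both arms alike and does not by itself bias the comparison between them. That point stands: what is at stake is the trial population and the screening record.

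On heparin, the printed figure is visibly malformed, three other statements agree with one another, and a text-extraction artefact cannot be fully excluded. The item would not warrant a mandatory correction on its own.

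On enoxaparin, the summary's therapeutic block is condensed throughout. It also leaves out the kidney-injury condition for unfractionated heparin and the creatinine-clearance condition for argatroban, both given in 3.1 and 7.7. The omission is abridgement, to be aligned when the text is next edited.

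**Conclusion.** The concern holds. The current text contains two D-dimer entry thresholds that differ by a factor of two, and no passage reconciles them. Patients at 700 to 1399 ng/mL are classified in opposite ways. How many patients that is cannot be derived from the documents. They also give no link between D-dimer level and mortality, so no effect on power or on the primary comparison is claimed. The conclusion rests on the printed figures and on one inference, that the 4.5 concentration and the 2.3 multiple describe the same criterion; the arithmetic supports it exactly.

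The D-dimer conflict alone is enough to require correction before sites rely on the text. The heparin figure is a secondary point: probably typographical, but in the operative dosing section, where leaving it uncorrected is an avoidable safety risk. The enoxaparin line is a minor alignment note. This review takes no position on which threshold or dose is right.

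**What to change.** Issue one short amendment that:

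1. states a single D-dimer entry threshold, in ng/mL and as a multiple of ULN, and makes 2.3, 4.2 and 4.5 agree, with the rationale in 2.3 supporting the threshold actually used;
2. checks the heparin figure in 7.7 against the approved source document and reconciles it with the summary, 2.2 and 3.1;
3. aligns the summary's therapeutic enoxaparin line with 2.2, 3.1 and 7.7.

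The sponsor decides which figures stand. If screening has already begun, the sponsor should also establish which D-dimer threshold was applied, so that the enrolled population and the screen-failure counts can be described correctly.

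The cost is a text amendment, its ethics board submission and distribution to sites. Design, sample size and data collection do not change.
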